PS#2: Funded by an International Society of Psychiatric Nursing Foundation Research grant (March 2017). The specific aims for this ongoing PS are to 1) assess the feasibility of using a community-engaged approach with FRs, 2) characterize the MH profile of Arkansas' FRs, and 3) explore individual FRs' perceptions of MH problems and use of MH services, including barriers and facilitators to help-seeking. *To achieve Aim 1*, the PI collaborated with PS#1 community partners to refine recruitment methods; these methods will be used in the proposed study (described below). Recruitment was successful and resulted in ample and continued access to this population, including presentations at four FR-related state conferences. *To achieve Aim 2*, FRs statewide were invited to complete an anonymous online survey that incorporated brief assessments of various MH problems,⁴² as well as questions addressing demographics and factors that can pose as potential risk/protective factors (e.g., marital status, military service).^{10,42} A total of 220 FRs started the survey and 87% completed it. Of completers, 86% were male and 95% were Caucasian; the average length of time as a FR was 16.2 years; 23% reported a previous MH diagnosis and 25% reported previous MH treatment. The high rates of self-reported MH problems found were: 26% for PTSD; 28% for moderate to severe anxiety; 14% for major (moderate-severe to severe) depression; 20% for harmful/ hazardous drinking; and, 34% for high-risk for suicidal behaviors, highlighting the need for the proposed study.

To achieve Aim 3, we conducted in-depth, ethnographic interviews with individual FRs. Thirty-two FRs were interviewed; of those interviewed, 36% reported a previous MH diagnosis,

Title: Building Partnerships with First Responders to Explore Strategies to Improve Delivery and Access of Mental Health Services

PI: [name], APRN

Institution: University of Arkansas for Medical Sciences

Sponsor: NIH/NIMH

and 40% reported previous MH treatment. Experience with Aim 3 demonstrates the willingness of FRs with MH problems to participate in qualitative research. Grounded theory-informed, qualitative analytic methods (as described below) were used to identify common themes. The main themes included: knowledge, barriers and facilitators to help-seeking, effects of the job and coping with them, non-duty stressors, pros and cons of existing MH services and delivery methods, and novel delivery approaches.

Specific Aims

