Phase 1-Specific Aim 1: Identify FRs' preferences and priorities regarding MH service and delivery methods, including the feasibility, acceptability, and value of each method.

Instruments and Measures

Prior to starting the focus group/interview, the PI or research associate (RA) will distribute a one-page document to reference during the informed consent process; the document will describe the study purpose, procedures, risks, and benefits (Human Subjects Protection); time will be allowed for questions. Participants will be advised that participating implies consent and they

Title: Building Partnerships with First Responders to Explore Strategies to Improve Delivery and Access of Mental Health Services

PI: [name], APRN

Institution: University of Arkansas for Medical Sciences

Sponsor: NIH/NIMH

may withdraw at any time. (We received a waiver of documentation of consent for the interviews in PS#2; we will seek the same for this study). Rules of confidentiality will also be discussed.

Following the consent process, participants will be asked to complete a brief form to collect data about demographics (i.e., age group, race/ethnicity, gender) and potential risk/protective factors (e.g., time in service, military service, medical problems).

The PI and/or RA will facilitate the focus group (FG) discussions using a semi-structured question guide (Table 2), which will have undergone review by our community partners. (In addition to content, we will ask them for feedback regarding language, ensuring it is non-stigmatizing.)

To start the group discussion, the PI/RA will use a PowerPoint presentation to highlight the various MH services discussed in the PS interviews. Group participants will be asked to discuss the pros and cons of existing MH services and delivery methods, and novel approaches that emerged during the interviews. They will be asked to discuss their own experiences related to each; based on their experiences, they will be asked to make recommendations for services/delivery methods that would motivate FRs to be more engaged in services. We will ask them “where to start” when implementing a MH service model; follow-up questions will include probes related to

Table 2. Qualitative Question Guide

Main Question	Which of these services and methods of delivery do you recommend?
Probe Questions	What do you like and not like about each of these services and delivery methods?

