	Do you foresee any additional barrier to using these services? Barriers to implementing them?
	Could they be modified/adapted to better fit the first responder culture and environment?
	Would you suggest any additional services or methods that we haven't discussed yet?
	What do you think we should start with first?

Title: Building Partnerships with First Responders to Explore Strategies to Improve Delivery and Access of Mental Health Services

PI: [name], APRN

Institution: University of Arkansas for Medical Sciences

Sponsor: NIH/NIMH

acceptability and feasibility. (Similar methods were effectively used in a study conducted by Co-investigator [name] and colleagues).⁵¹

In concluding the FGs, we will offer optional telephone follow-ups to participants who may be reluctant to express their views in the group. Participants will also receive a blank piece of paper, along with a web link to an anonymous form in Survey Monkey. Here, they can add information they may not be comfortable discussing in the FG; text data from these options will be included in data analysis. Additionally, the PI/RA will record field notes during each FG, noting information about context, nonverbal communication, and interactions observed during the FG.⁵²

Research Team

The PI is psychiatric advanced practice registered nurse whose qualifications to serve as PI on this project stem from: 1) well-established community partnerships with FRs across the state; 2) having completed a systematic review and pilot studies related to the MH of FRs^{36, 37}; 3) previous clinical and research experience with individuals that have experienced trauma; and, 4) interdisciplinary collaboration with experts in the fields of emergency medical services and qualitative research. Co-I [name] is an expert in qualitative methods. She will attend monthly team meetings to evaluate the FG processes, including development of the FG question guide and assist in qualitative data analysis (as described in Data Management and Analysis section). Co-I [name] is an expert in implementation science and has conducted multiple qualitative studies related to help-seeking and use of MH services. He will attend monthly team meetings regarding these aspects of study implementation, including the FG method (which was

Title: Building Partnerships with First Responders to Explore Strategies to Improve Delivery and Access of Mental Health Services

PI: [name], APRN

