Sampling and Sample Size. An essential part of grounded theory-informed methods is the use of theoretical sampling.⁴⁹ In grounded theory research, we do not know the important themes in advance; instead, they emerge and are refined over time as data are collected and analyzed. In general, exploration of a certain theme is stopped when “saturation” is reached, that is, no new themes emerge from the data (discussed below). Therefore, theoretical sampling does not provide a detailed sampling schema or calculation for number of participants beforehand. For this study, we will recruit FRs to participate in up to 25 FGs that will include 5-12 participants per group. Eighteen of these groups will be open to all FRs from different regions across the state. Evidence suggests that call volume and career vs. volunteer service influence FRs’ MH.⁴² The 2 most populous regions in Arkansas (Central and Northwest) have higher EMS call volumes and a greater number of career fire/ambulance services than the other 4 regions; the

Title: Building Partnerships with First Responders to Explore Strategies to Improve Delivery and Access of Mental Health Services

PI: [name], APRN

Institution: University of Arkansas for Medical Sciences

Sponsor: NIH/NIMH

latter are more rural and are served primarily by volunteer fire/ambulance services (Figure 2).

Therefore, we propose to conduct 1) five FGs in each of the two most populous regions

(total=10), and 2) two FGs in each of the other four regions (total=8).

Since the majority of FRs are white males,^{1,62} female and minority FRs may be reluctant to openly discuss MH-related issues in a diverse group. We will conduct a minimum of 2 of the 25 FGs with an ethnically diverse group of females only, and an additional 2 FGs with minorities only (males and females) (total=4). This will ensure that at least 10-15% of participants are females and minorities. We will make every effort to recruit these participants from across AR, but due to the distribution of FRs across AR, we expect these FGs will take place in Central and Northwest AR.

Sample Size

An essential part of qualitative methods is the use of theoretical sampling. Theoretical sampling does not provide a detailed sampling schema or calculation for number of participants beforehand. Instead, exploration of a certain theme is stopped when “saturation” is reached, that is, no new themes emerge from the data (see Analysis section).

Compensation

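### In the focus groups no open question precedes the service slides and the coding does not separate prompted from spontaneous mentions, so the relative frequency of listed services may partly reflect the slides

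*Combined protocol and SAP*

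**What the plan says.** Under Phase 1, Instruments and Measures, the group session runs from consent to a short background form and then to the slides: "To start the group discussion, the PI/RA will use a PowerPoint presentation to highlight the various MH services discussed in the PS interviews". Participants next weigh the existing services and the novel approaches that came out of those interviews, describe their own experience, and make recommendations. The main question in Table 2 is "Which of these services and methods of delivery do you recommend". The fourth of its five probes is "Would you suggest any additional services or methods that we haven't discussed yet" and the fifth is "What do you think we should start with first". At the close, participants are offered a telephone follow-up, blank paper and an anonymous web form, and text from these options is analysed.

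The source of the list is described in Preliminary Studies, PS#2: "To achieve Aim 3, we conducted in-depth, ethnographic interviews with individual FRs", and "Thirty-two FRs were interviewed". The themes found there included novel delivery approaches.

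Sampling and Sample Size says of grounded theory research that "we do not know the important themes in advance; instead, they emerge and are refined over time as data are collected and analyzed". Data Analysis lets new codes be added and earlier transcripts recoded. The Saturation paragraph plans a table of thematic categories with the frequency of explanations and example text.

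**The concern.** Aim 1 asks for preferences and priorities as well as an appraisal of each method. The instrument suits the appraisal. It suits the priorities less well, because what people name unaided can no longer be observed once a list has been shown. A service on the slides is put before every group by design, while one that is not on them has to be volunteered. If the theme table counts both kinds of mention alike, a listed service can look more prominent than unaided discussion would have made it.

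The Delphi is where this would matter. Its first meeting reviews the recommendations and priorities from Aim 1, so any prominence due to the slides would enter the consensus process as a finding.

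**Working it through.** No sample-size or error-rate arithmetic bears on this point. The check is of order, wording and coding, followed by a count of how many groups are affected.

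1. **Order.** Between the background form and the slides, the protocol describes no question that asks for views. The guide is semi-structured, so the probes may move, but the slides are fixed at the start of the discussion.

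2. **Wording.** The main question points back to the services shown. The first three probes (likes and dislikes, barriers, adaptation) do the same. The fourth probe is open to additions and the fifth is fairly open on priority, but both follow the slides. So do the telephone, paper and web routes, which are offered for views that people may be reluctant to voice in the group.

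3. **Coding.** Top-level coding, second-level coding and the Saturation paragraph describe no tag for prompted or spontaneous mentions and none for on-list or off-list services. An on-list or off-list tag could be added later from the transcripts and the slide file. A before-or-after tag could not: with the slides first, every service mention in the discussion falls after them. That information is lost unless the session itself changes.

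4. **Extent.** Five groups in each of two regions gives 2 × 5 = 10. Two groups in each of four regions gives 4 × 2 = 8. Two female-only and two minority-only groups give 4. The total is 10 + 8 + 4 = 22. This agrees with the range of 132-220 in the Saturation paragraph if groups hold 6 to 10 people: 22 × 6 = 132 and 22 × 10 = 220. The plan allows up to 25 groups. The slide step is described for group discussions without exception.

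5. **What the count leaves out.** The Saturation paragraph also lists 44 individual interviews. The protocol does not say whether these open with slides, so they are not counted as exposed.

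6. **Onward use.** At the initial Delphi meeting, a handout describes existing services and the research associate reviews the Aim 1 recommendations and priorities. Nothing described would tell the panel which of these arose before prompting.

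**The case against.** The strongest reply is that the design is sequential and deliberate. First responders' views were explored individually in PS#2, and the groups then appraise what was raised. Appraising each method is part of Aim 1 and requires the methods to be shown. The pros-and-cons discussion and the probe on likes and dislikes leave room to reject what is listed. The sentence about themes not being known in advance explains the absence of a sample-size calculation and makes no promise about question order. Community partners will review the guide, and a co-investigator expert in qualitative methods will evaluate the focus-group process, including the guide's development. The frequency table is described as an audit trail, not as an estimate of prevalence.

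Most of this stands, and it rules out several stronger readings that a reader might infer:

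- **That the list is the investigators' own.** The items came from 32 first responders, although the team chooses what to highlight.
- **That ideas outside the list are lost.** Participants are asked for additions, the free text is analysed, and new codes can be created.
- **That anchoring is shown to occur, or that saturation will be an artefact of the slides.** The documents contain no evidence on either. Counting exposed groups does not measure bias.
- **That all Phase 1 data are affected.** The individual interviews are not said to use the slides.

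The reply does not meet the narrower point. The earlier interviews had the stated aim of exploring perceptions of mental health problems and service use, including barriers and facilitators to help-seeking; ranking priorities was not part of it. The sex and race of the 32 interviewees are not given, so one cannot check whether the list reflects the women and minority responders for whom separate groups are planned. Justifying a list does not justify showing it before any open question.

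**Conclusion.** The point holds as a limited gap in elicitation and coding. Within the focus groups, participants' top-of-mind priorities cannot be separated from prompted ones, so the relative frequency of listed services in the theme table may partly reflect the slides and pass into the Delphi.

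The procedure covers all 22 itemised groups, or up to 25 if the maximum is run. The size of any distortion is unknown and cannot be derived from the documents. The conclusion assumes that the sessions follow the described order and that no unreported warm-up question is asked. It does not call into question the use of a list or the recording of off-list ideas. This is a worthwhile, inexpensive improvement rather than a flaw that undermines Phase 1. It is best made before data collection, because the unprompted response cannot be recovered afterwards.

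**What to change.** - Before the slides, ask one open question for about 5-10 minutes: what help, delivered how, first responders would actually use, and what should come first. Then show the slides and continue with Table 2 as planned.
- Tag each service mention as before or after the slides, and as on or off the list. Show these categories separately in the planned data table and in the Aim 1 summary given to the Delphi panel.
- Optionally, begin the main question with *Which, if any, of these*, so that recommending none is plainly allowed.
- State whether the individual interviews open with the slides.

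The cost is 5-10 minutes less slide-led discussion per group, a small coding burden, and a revised guide for partner and IRB review. The appraisal of each method is kept.

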Institution: University of Arkansas for Medical Sciences

Sponsor: NIH/NIMH

successfully used in his previous studies). The RA is a licensed social worker (LCSW) with over 10 years' experience, and a local volunteer firefighter.

Study Population

Participants will include a convenience sample of firefighters and EMTs/paramedics from across Arkansas.

Inclusion criteria

- ages 18 and over;
- volunteer and career personnel;
- active, inactive, and retired

Exclusion criteria

- Non-english speaking (due to the nature of FG/interview discussions).

Recruitment

We will use opt-in methods, facilitated by our community partners, to recruit participants.

The PI will visit recruitment sites, provide refreshments, distribute promotional materials, and discuss long-term study goals. She will send emails to community partners that include study information, invitations to participate, and suggested text for email reminders.⁵⁰ Partners will then distribute the emails throughout their departments; the State EMS Director will distribute through the state EMS registry, which includes all certified EMT/paramedics in the state. Emails and promotional

Figure 2: Arkansas: Regional Map

Title: Building Partnerships with First Responders to Explore Strategies to Improve Delivery and Access of Mental Health Services

PI: [name], APRN

Institution: University of Arkansas for Medical Sciences

Sponsor: NIH/NIMH

materials will instruct FRs to contact the PI or research assistant (RA) by telephone for more study information. They will also have the option to follow a web link (available as a Quick Response [QR] code) where they can read more about the study and/or submit their name (first name, last initial), phone number and/or email address to be contacted with more study information. They will also be asked which region of the state they respond in; no additional information will be requested online.

Many community partners are involved in FR-related organizations; she may be invited to present and recruit at state meetings. Some of the departments also distribute monthly/ quarterly newsletters; study information will be published therein (with approval from the administration). The flyer will also be placed on social media sites, such as Facebook and Instagram.

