The PI will carefully monitor study procedures to protect the safety of research subjects, the quality of the data and the integrity of the study. All data will be recorded without identifiers and will be anonymous. Audio-recordings will be stored in a locked filing cabinet and all transcriptions will be electronically documented. All electronic data will be maintained on a password-protected UAMS server, both located behind locked doors in a restricted access area of the UAMS campus. Only the PI, Co-Is, and Research Assistant (to be determined) will have access to the data.

Data Analysis

The RA will enter quantitative participant data (i.e. demographics, risk/protective factors) into SPSS (V24).⁵³ Data will be analyzed using standard statistical techniques to summarize data distributions and to model associations among risk and status variables. FGs and interviews will be audio recorded, transcribed verbatim, and entered into a professional software program designed to facilitate the data analysis process and produce an audit trail.⁵⁴ Data submitted online will also be entered.

We will analyze data using grounded theory-informed methods of content analysis and constant comparison.⁴³ Content analysis is a systematic, objective analysis designed to identify key words, phrases, and topics, which guides *top-level coding*.⁵⁵ This process is followed by constant comparison, *second-level coding*, an iterative process designed to identify common

Title: Building Partnerships with First Responders to Explore Strategies to Improve Delivery and Access of Mental Health Services

PI: [name], APRN

Institution: University of Arkansas for Medical Sciences

Sponsor: NIH/NIMH

themes by comparing one set of data to another.⁴⁹ We will also use this process to compare data across sub-groups (e.g. urban/rural, male/female). The PI has experience in qualitative methods; both co-Is have expertise in qualitative methods; and the RA will be trained in these methods.

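### Does the planned modelling of participant-form data lack an outcome and understate its standard errors because participants sit in focus groups?

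*Combined protocol and SAP*

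**What the plan says.** The Data Analysis section gives two sentences to the quantitative data. The first covers entry: "The RA will enter quantitative participant data (i.e. demographics, risk/protective factors) into SPSS (V24"). The second covers analysis: "Data will be analyzed using standard statistical techniques to summarize data distributions and to model associations among risk and status variables". The rest of that section, with its coding and saturation paragraphs, is qualitative.

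Instruments and Measures describes the source. "Following the consent process, participants will be asked to complete a brief form to collect data" on "demographics (i.e., age group, race/ethnicity, gender") and on "potential risk/protective factors (e.g., time in service, military service, medical problems"). The form itself is not reproduced.

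Study Population states: "Participants will include a convenience sample of firefighters and EMTs/paramedics from across Arkansas". It admits volunteer and career personnel, whether active, inactive or retired. Sampling and Sample Size plans "up to 25 FGs that will include 5-12 participants per group". It itemises ten groups in the two most populous regions, eight in the other four, and at least two female-only and two minority-only groups. The Saturation paragraph expects 132 to 220 people in focus groups and 44 individual interviews.

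Under Specific Aims, Aim 1 is answered by qualitative interviews and Aim 2 by a virtual Delphi process.

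**The concern.** The data are described as "quantitative participant data (i.e. demographics, risk/protective factors"), and status is not one of those categories. No symptom scale, mental-health diagnosis, treatment or service-use item is named for the Phase 1 form, whereas the earlier survey described under Preliminary Studies did collect such measures. A reader cannot tell what would be regressed on what.

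The sampling adds a second worry. Participants volunteer through departments and sit in groups formed by region and, for some groups, by sex or minority status. If people in the same group resemble each other, a model that treats them as independent overstates precision for any factor that follows group lines. Self-selection could also distort the associations. At stake would be spurious findings reported from an analysis whose outcome was chosen after the data were seen.

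**Working it through.** **Expected sample.** The itemised groups are 10 + 8 + 2 + 2 = 22. At 6 to 10 people each, 22 × 6 = 132 and 22 × 10 = 220, which matches the Saturation paragraph. The stated group size of 5 to 12 would instead give 110 to 264 for 22 groups, or 125 to 300 for 25. That is a separate inconsistency and does not affect this point. The plan gives no sample size, precision or intraclass correlation (ICC) for any association model.

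**Is a status variable absent?**
- In Data Analysis, the closed list (i.e.) names categories of data, not items.
- In Instruments and Measures, the demographic list is closed, but the risk/protective list is open (e.g.) and includes medical problems.
- Preliminary Studies gives marital status as an example of a risk/protective factor in the earlier survey. It also reports previous diagnosis (36%) and treatment (40%) for the 32 people interviewed then.
- Study Population distinguishes career from volunteer and active from retired personnel, which is also a kind of status.

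The documents therefore identify no status variable, but they do not show that none is collected.

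**Covariate constant within groups.** The design effect is DE = 1 + (m − 1) × ICC, where m is the group size. The ratio of naive to true standard error (SE) is 1/√DE. The true error rate of a nominal two-sided 5% test is 2 × [1 − Φ(1.96/√DE)]. The ICC values are assumptions.

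| m | ICC | DE | Naive/true SE | True error rate |
|---|---|---|---|---|
| 6 | 0.01 | 1.05 | 0.976 | 5.6% |
| 6 | 0.05 | 1.25 | 0.894 | 8.0% |
| 6 | 0.10 | 1.50 | 0.816 | 11.0% |
| 10 | 0.01 | 1.09 | 0.958 | 6.0% |
| 10 | 0.05 | 1.45 | 0.830 | 10.4% |
| 10 | 0.10 | 1.90 | 0.725 | 15.5% |

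The understatement runs from 1 − 0.976 = 2.4% to 1 − 0.725 = 27.5%. A wider assumption of m = 8 and ICC 0.02 to 0.20 gives DE 1.14 to 2.40, an understatement of 6 to 35%, and error rates of 6.6 to 20.6%. At ICC 0 there is none.

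**Covariate varying within groups.** Here DE = 1 + (m − 1) × ICC_x × ICC_y, with one ICC for the covariate and one for the outcome. With both at 0.05 to 0.10:
- m = 6: DE runs from 1 + 5 × 0.0025 = 1.0125 to 1 + 5 × 0.01 = 1.05.
- m = 10: DE runs from 1 + 9 × 0.0025 = 1.0225 to 1 + 9 × 0.01 = 1.09.

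The true SE is therefore √1.0125 = 1.006 to √1.09 = 1.044 times the naive one, or about 1 to 4% larger. If the covariate is fully balanced within groups, ICC_x = −1/(m − 1). Then DE = 1 − ICC_y, which is 0.90 to 0.95 for ICC_y of 0.05 to 0.10, and the naive SE is slightly too large.

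**Which case applies?** Age group, time in service, military service and medical problems can all differ between people in the same group. Urban/rural setting does follow group lines, but Data Analysis assigns that comparison to the qualitative constant-comparison process. Sex and minority status are fixed by design in only 4 of the 22 itemised groups. The form appears to be completed before discussion starts, so group interaction would not create the correlation. The 44 individual interviews are not group sessions. If they are separate people, they make up 44/176 = 25% to 44/264 = 17% of the data and dilute the effect further.

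**The case for a change.** The strongest case for a change is that the sentence cannot be carried out as written. It names no outcome, predictors or model and carries no exploratory label, so every choice is left until after the data are seen. Neither aim needs the analysis, and limiting the form data to descriptive summaries would take one sentence and cost neither aim anything. Where a covariate does follow group lines, the inflation is real: up to 15.5% for a nominal 5% test at 10 per group and ICC 0.10.

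Much of this stands. The status variable is undefined, the models are unspecified and no handling of clustering is described. Three parts do not carry through. Open-ended form content does not prove that an outcome is missing. Convenience sampling limits generalisability and can bias associations, but it neither removes an outcome nor shrinks standard errors. The error rates describe a hypothesis test that the plan never commits to, and its reference to standard techniques does not exclude a cluster adjustment. That neither aim needs the models also counts against a change, because it limits the harm.

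**Conclusion.** No change to the plan is needed. This is an undefined term and an unspecified exploratory model in a qualitative study. Analysts can fill the gap by stating which form item they treat as status, describing the sample, and labelling any comparison exploratory, with attention to grouping where a covariate follows group lines.

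If grouping were ignored, the understatement would be about 2 to 28% of the standard error for covariates fixed within groups. For the kind of item actually named on the form, the true standard error would be about 1 to 4% larger. Both figures rest on 6 to 10 people per group and assumed ICCs of up to 0.10; a larger ICC would raise them. The themes, saturation judgements and 75% Delphi consensus rule do not depend on these models, so the conclusions for both aims stand whatever the models show.
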